5.2 Exclusion Criteria

Subjects ***may not*** enter the study if they fulfill any of the following criteria:

1.	Prior exposure to doxorubicin, PLD or any other anthracycline, motolimod and other TLR agonists (pre Amendment 2), MEDI4736 or checkpoint inhibitors, such as anti-CTLA4 and anti-PD1/anti-PD-L1 antibodies.
2.	Subjects with platinum-refractory disease, defined as disease progression while receiving first line platinum-based therapy.
3.	Clinically significant persistent immune-related adverse events following prior therapy.
4.	Subjects with history or evidence upon physical examination of CNS disease, including primary brain tumor, seizures not controlled with standard medical therapy, any brain metastases, or, within six months prior to Day 1 of this study, history of cerebrovascular accident (CVA, stroke), transient ischemic attack (TIA) or subarachnoid hemorrhage.
5.	Subjects with clinically significant cardiovascular disease. This includes: 
 a. Resistant hypertension. b. Myocardial infarction or unstable angina within 6 months prior to Day 1 of the study. c. History of serious ventricular arrhythmia (i.e., ventricular tachycardia or ventricular fibrillation) or cardiac arrhythmias requiring anti-arrhythmic medications, except for atrial fibrillation that is well controlled with anti-arrhythmic medication. d. Baseline ejection fraction \leq 50% as assessed by echocardiogram or MUGA. e. New York Heart Association (NYHA) Class II or higher congestive heart failure. f. Grade 2 or higher peripheral ischemia, except for brief (< 24 hrs) episodes of ischemia managed non-surgically and without permanent deficit.
6.	History of pneumonitis or interstitial lung disease.
7.	Active, suspected or prior documented autoimmune disease (including inflammatory bowel disease, celiac disease, Wegner's granulomatosis, active Hashimoto's thyroiditis, rheumatoid arthritis, lupus, scleroderma and its variants, multiple sclerosis, myasthenia gravis). Vitiligo, type I diabetes mellitus, residual hypothyroidism due to autoimmune condition only requiring hormone replacement, psoriasis not requiring systemic treatment, or conditions not expected to recur in the absence of an external trigger are permitted.
8.	Other malignancy within 2 years prior to Day 1 of the study, except for those treated with surgical intervention only.
9.	Subjects with clinical symptoms or signs of gastrointestinal obstruction and/or who require drainage gastrostomy tube and/or parenteral hydration or nutrition.
10.	Known immunodeficiency or HIV, Hepatitis B or Hepatitis C positivity.
11.	History of severe allergic reactions to any unknown allergens or components of the study drugs.

CONFIDENTIAL

12.	Other serious illnesses (e.g., serious infections requiring antibiotics, bleeding disorders).
13.	Prior treatment in any other interventional clinical trial within 4 weeks prior to Day 1 of the study.
14.	Mental impairment that may compromise compliance with the requirements of the study.
15.	Lack of availability for immunological and clinical follow-up assessment.
16.	Women of child bearing potential who are found to be pregnant as evidenced by positive serum pregnancy test (minimum sensitivity 25 IU/L or equivalent units of HCG) or nursing. NOTE: Pregnancy tests are not required for subjects who are not of child-bearing potential as defined in #17.
17.	
Female subjects of childbearing potential who are sexually active with a nonsterilized male partner must use at least one highly effective method of contraception (see table below) from screening, and must agree to continue using such precautions for 90 days after the final dose of investigational product (MEDI4736). Male partners of a female subject must use male condom plus spermicide throughout this period (from screening and for 90 days after subject's receipt of the final dose of investigational product). Cessation of birth control after this point should be discussed with a responsible physician. Not engaging in sexual activity for the total duration of the trial and the drug washout period is an acceptable practice; however, periodic abstinence, the rhythm method, and the withdrawal method are not acceptable methods of birth control. Female subjects should refrain from breastfeeding throughout the period described above.
 
NOTE: For the standard of care, pegylated liposomal doxorubicin (PLD, Doxil[®], Caelyx[®]), the package insert advises females of reproductive potential to use effective contraception during and for 6 months after last treatment with the drug. Therefore, all subjects of childbearing potential on this study should continue contraception use for 6 months after the last PLD administration.
 
Females of childbearing potential are defined as those who are not surgically sterile (i.e., bilateral tubal ligation, bilateral oophorectomy, or complete hysterectomy) or post-menopausal.
 
Females will be considered post-menopausal if they have been amenorrheic for 12 months without an alternative medical cause. The following age-specific requirements apply:
 
 • Females <50 years of age would be considered post-menopausal if they have been amenorrheic for 12 months or more following cessation of exogenous hormonal treatments and if they have luteinizing hormone and follicle-stimulating hormone levels in the post-menopausal range for the institution or underwent surgical sterilization (bilateral oophorectomy or hysterectomy). • Females ≥50 years of age would be considered post-menopausal if they have been amenorrheic for 12 months or more following cessation of all exogenous hormonal treatments, had radiation-induced menopause with last menses >1 year ago, had chemotherapy-induced menopause with last menses >1 year ago, or underwent surgical sterilization (bilateral oophorectomy, bilateral salpingectomy or hysterectomy).

CONFIDENTIAL

Highly effective methods of contraception are described in the table below. A highly effective method of contraception is defined as one that results in a low failure rate (i.e., less than 1% per year) when used consistently and correctly. Note that some contraception methods are not considered highly effective (e.g. male or female condom with or without spermicide; female cap, diaphragm, or sponge with or without spermicide; non-copper containing intrauterine device; progestogen-only oral hormonal contraceptive pills where inhibition of ovulation is not the primary mode of action [excluding Cerazette/desogestrel which is considered highly effective]; and triphasic combined oral contraceptive pills). Acceptable highly effective methods of contraception are described in the following table:

Highly Effective^a Methods of Contraception	
Barrier/Intrauterine Methods	Hormonal Methods

 • Copper T intrauterine device • Levonorgestrel-releasing intrauterine system (e.g., Mirena[®])^b 	
 • Implants: Etonogestrel implants: e.g. Implanon or Norplan • Intravaginal device: ethinylestradiol and etonogestrel- releasing intravaginal devices: e.g. NuvaRing[®] • Injection: Medroxyprogesterone injection: e.g. Depo-Provera • Combined Pill: Normal and low dose combined oral contraceptive pill • Patch: Norelgestromin/ethinylestradiol-releasing transdermal system e.g. Ortho Evra[®] • “Minipill^c”: Progesterone based oral contraceptive pill using desogestrel e.g., Cerazette[®]

a - Highly effective (i.e. failure rate of <1% per year) b - This is also considered a hormonal method c - Cerazette[®] is currently the only highly effective progesterone based pill
	

18.	Any condition that, in the clinical judgment of the treating physician, is likely to prevent the subject from complying with any aspect of the protocol or that may put the subject at unacceptable risk.
19.	Subjects must not donate blood while on study and for at least 90 days following the last MEDI4736 treatment.
20.	History of allogeneic organ transplant

5.3 Restrictions on Concomitant Therapies

5.3.1 Non-Permitted Concomitant Therapies

Subject **may not** receive the following concomitant therapies during the study:

1.	Systemic treatment with glucocorticosteroids or other immunosuppressive treatments (e.g., methotrexate, chloroquine, azathioprine). See Section 5.3.2 for exceptions. (Wash-out period: 2 weeks prior to Day 1).
2.	Other cancer therapy (e.g., drug, radiation or immunotherapy). Wash-out period: 4 weeks or 5 half-lives (whichever is shorter) prior to Day 1; 6 weeks for nitrosoureas.
3.	Live/attenuated vaccines 1 month prior to Day 1 and for at least 6 months after the last dose of treatment.
The wash-out period prior to Day 1 of the study for all non-permitted drugs should be at least 1 week, unless stated otherwise above.	

5.3.2 Permitted Concomitant Therapies

Subject **may** receive the following concomitant therapies during the study:

1.	Intranasal or inhaled steroids for treating mild to moderate asthma or allergies, physiological steroid replacement, intra-articular steroids, or topical steroids for localized dermatitis (<5% of BSA).
2.	NSAIDs, acetylsalicylic acid and specific COX-2 inhibitors.
3.	Antihistamines and other non-steroidal anti-allergy medication.
4.	Hormone replacement therapy.
5.	Palliative radiation of non-target and/or non-index lesions, or for symptom management.
6.	At the discretion of the Investigator, any drug or non-drug therapy necessary to treat any condition arising during the study, including high dose corticosteroids or anti-TNF agents (e.g. infliximab) to treat immune-mediated adverse reactions. Subjects should receive full supportive care, including transfusions of blood and blood products, and treatment with antibiotics, anti-emetics, anti-diarrheal, and analgesics, and other care as deemed appropriate, and in accordance with their institutional guidelines. Use of anticoagulants such as warfarin is permitted however, caution should be exercised and additional International Normalized Ratio (INR) monitoring is recommended. [Note: Motolimod should not be dosed within 24 hours of systemic corticosteroid use. Doses of motolimod should be delayed or skipped as appropriate. See Sections 8.2, 8.3, and 8.4 regarding dose delays.] PER Amendment 2, motolimod dosing will be discontinued for all subjects.
All prescription and nonprescription drugs must be recorded in the concomitant medications section of the case report form, listing generic (preferably) or brand name, indication, dose, route and dates of administration. All non-drug therapies must be recorded in the respective sections of the case report form.	

CONFIDENTIAL

6 Study Drug Preparation and Administration

6.1 Pegylated Liposomal Doxorubicin (PLD)

Pegylated liposomal doxorubicin (PLD) is commercially available and will be ordered by the pharmacy at the investigative site.

Please refer to the package insert for PLD for the most current formulation, preparation and administration. The dose to be administered is 40 mg/m², which is consistent with current clinical practice.

Maximum body surface area for PLD dose calculations will be 2.0 m². Dose recalculation for each cycle will be needed if there is a weight change > 10%. NOTE: The maximum body surface area and recalculations are recommendations; standard procedures for maximum body surface and recalculations at each site may be used.

6.2 Motolimod

PER Amendment 2, motolimod dosing will be discontinued for all subjects.

Motolimod is supplied by the Sponsor. Prior to administration, motolimod must be reconstituted using sterile water for injection. Please see to section 6.2.2 for preparation and administrative instructions.

6.2.1 Motolimod Study Drug Information

Manufacturer	VentiRx		
Expiration/Retest Date	Expiration/retest dates are documented on the Certificate of Analysis and/or stability certification.		
Container Description	Type: Single use vial	Material: clear-glass	Size: 3-mL
Formulation	Motolimod is supplied as an off-white, lyophilized cake and is comprised of an active pharmaceutical ingredient (VTX-378) formulated with a solubilizing agent at neutral pH.		
Active Ingredient Content	Mass/Weight: 8.4mg	Volume: n/a	Concentration: 10mg/mL when reconstituted with 0.7mL sterile water
Storage Conditions	2°C–8°C (26°F–46°F)		
Stability after reconstitution	24 hours at 2-8°C or 8 hours at ambient		
Labeling	Product name, lot number, route of administration, and storage conditions		

6.2.2 Motolimod Preparation

Prior to administration, motolimod must be reconstituted using sterile water for injection, USP. Reconstituted stock solutions are stable for 8 hours at room temperature and for 24 hours when

CONFIDENTIAL

refrigerated at 2–8°C. Motolimod should be prepared and transferred using aseptic technique in a biological safety cabinet. Vials of motolimod are intended for single use only.

1. Determine the appropriate dose based on the subject's BSA.
 - a. Calculate the total dose to be administered:
BSA (__. __ m²) x dose level (__. __ mg/m²) = total dose (__. __) mg) of motolimod.
 - b. Calculate the dose volume:
Total dose (__. __) mg.) ÷ 10 mg/mL = dose volume (__. __ mL) of motolimod.
2. Reconstitute 1 vial of motolimod with 0.7 mL Sterile Water for Injection
3. Sterile Water for Injection, as described below, to yield 0.84 mL of solution with a concentration of 10 mg/mL.
 - a. Add the sterile water for injection while directing the stream at the lyophilized cake.
 - b. Swirl the vial to disperse the water throughout the cake
 - c. Invert the vial repeatedly for approximately 2–3 minutes until the contents are fully dissolved. The reconstituted solution should be clear, and will range in color from colorless to yellow.
4. Using a syringe appropriate for subcutaneous dosing to draw up __. __ mL (dose volume; step 1b) from the vial of 10 mg/mL motolimod.

6.2.3 Motolimod Administration

On days with concurrent motolimod and MEDI4736 dosing, motolimod administration will occur 30-60 minutes after the end of the MEDI4736 infusion. Motolimod is administered as a subcutaneous injection. Within 30 minutes prior to each dose of motolimod, subjects will be administered 650–1000 mg acetaminophen by mouth to help mitigate potential adverse events commonly associated with the administration of motolimod (e.g., fever, myalgia). Subjects will be given or instructed to take an additional dose of 650–1000 mg acetaminophen by mouth approximately 4–6 hours after administration of motolimod, and as needed thereafter for symptoms of fever and/or body aches. Acetaminophen is the preferred over-the-counter analgesic and antipyretic; due to their potentially immunosuppressive effects, administration of NSAIDS within 24 hours of dosing should be avoided if clinically feasible.

To potentially reduce the effects of injection site reaction that may be associated with the administration of motolimod, an ice pack may be applied to the injection site for approximately 30 minutes prior to injection, immediately following injection, and throughout the day of injection. Additionally, at the discretion of the Investigator, single doses of motolimod may be divided and administered at two different anatomical locations.

The dose of motolimod should be administered with a syringe suitable for subcutaneous injection. To administer the injection, 1–2 inches of fatty tissue should be pinched up to avoid injection into the muscle layer. The needle can be inserted at either 45 or 90 degrees; a 45 degree angle is recommended when less than 2 inches of tissue can be pinched. Appropriate anatomic areas for subcutaneous injection include the fatty tissue over the abdomen, triceps, thighs, or lower back. The injection site should be rotated among anatomically appropriate locations to help avoid injection site reaction.

Standard medications to treat possible hypersensitivity reactions and/or symptoms of cytokine release syndrome (CRS) should be readily available at the time of treatment, including

CONFIDENTIAL

epinephrine, H1 antihistamines (e.g., diphenhydramine), H2 antihistamines (e.g., ranitidine), narcotics, IV fluids for volume expansion and supplemental oxygen.

Due to their immunosuppressive effect, administration of systemic corticosteroids (e.g., dexamethasone) should be avoided in this setting if other means of treatment are available and appropriate. If systemic corticosteroid use is clinically necessary, motolimod should not be administered within 24 hours. Doses of motolimod should be delayed or skipped as appropriate.

6.3 MEDI4736

MEDI4736 is supplied by the Sponsor. Commercially available 0.9% (w/v) saline or 5% (w/v) dextrose will be supplied by each site. Please see Section 7.2.8, for additional details.

6.3.1 MEDI4736 Study Drug Information

Manufacturer	MedImmune		
Expiration/Retest Date	Expiration/retest dates are documented in the QA Disposition of Investigational Medicinal Product (IMP) Report.		
Container Description	Type: Single use vial	Material: glass	Size: 10 mL
Formulation	Liquid solution containing 500 mg MEDI4736 per vial. The solution contains 50 mg/mL MEDI4736, 26 mM histidine/histidine-HCl, 275 mM trehalose dihydrate, 0.02% (weight/volume [w/v]) polysorbate 80, at pH 6.0.		
Active Ingredient Content	Mass/Weight: 500 mg	Volume: 10 mL	Concentration: 50 mg/mL
Storage Conditions	2°C to 8°C (36°F to 46°F) Do not freeze		
Labeling	Product name, lot number, route of administration, and storage conditions		

6.3.2 MEDI4736 Investigational Product Inspection

Each vial of MEDI4736 selected for dose preparation should be inspected. If there are any defects noted with the investigational product (IP), the Investigator and Sponsor should be notified immediately.

6.3.3 MEDI4736 Preparation

Preparation of MEDI4736 and preparation of the intravenous bag are to be performed aseptically by the IP manager or designated personnel. No incompatibilities between MEDI4736 and polyvinylchloride or polyolefin copolymers have been observed.

CONFIDENTIAL

6.3.3.1 MEDI4736 Preparation for Cohort at Dose Level 0a

Dose Calculation:

The volume of MEDI4736 (in mL) to add to the IV bag is calculated as follows:

Volume of MEDI4736 (mL)	=	Dose (mg/kg) X	Subject Weight (kg) ÷	MEDI4736 Concentration (nominal 50 mg/mL)
----------------------------	---	----------------	-----------------------	---

The corresponding volume of MEDI4736 should be rounded to the nearest tenth mL (0.1 mL). Dose adjustments for each cycle are only needed for a greater than 10% change in weight.

Dose Preparation:

MEDI4736 will be administered using a 250 mL IV bag containing 0.9% (w/v) saline or 5% (w/v) dextrose. A volume of diluent equal to the calculated volume of MEDI4736 to be added to the IV bag must be removed from the bag prior to addition of MEDI4736. The calculated volume of MEDI4736 is then added to the IV bag, and the bag is mixed by gentle inversion to ensure homogeneity of the dose in the bag.

Example: For a subject weighing 80 kg and dosed at 10 mg/kg, 16 mL [10 mg/kg x 80 kg divided by 50 mg/mL] of MEDI4736 is to be diluted in a 250 mL IV bag. First, 16.0 mL of diluent is removed from the IV bag, and then 16 mL of MEDI4736 is added to the bag. The bag is mixed by gentle inversion to ensure homogeneity of the dose in the bag.

Per Amendment 3, fixed dosing will be used for the optional study treatment extension as described in Section 3.1.12 and Section 8.9. See Section 6.3.3.2.

6.3.3.2 MEDI4736 Preparation for all Subjects except Cohort at Dose Level 0a and for Treatment Extension

Per Amendment 3, fixed dosing will be used for all subjects who proceed with the optional study treatment extension as described in Section 3.1.12 and Section 8.9.

Dose Calculation:

Subjects will receive a fixed dose of MEDI4736: 1500 mg Q4W for subjects > 30 kg. If a subject's body weight drops to ≤ 30 kg while on the study, the subject will receive weight-based dosing equivalent to 20 mg/kg Q4W for MEDI4736 as long as the body weight remains ≤ 30 kg (e.g., a 30 kg subject would receive a 600 mg dose; a 25 kg subject would receive a 500 mg dose; etc.). When the weight improves to >30 kg, the subject may return to fixed dosing of MEDI4736 1500 mg.

The volume of MEDI4736 (in mL) to add to the IV bag is calculated as follows:

Volume of MEDI4736 (mL)	=	Dose (mg)	÷	MEDI4736 Concentration (nominal 50 mg/mL)
----------------------------	---	-----------	---	--

Dose Preparation:

MEDI4736 will be administered using a 250 mL IV bag containing 0.9% (w/v) saline or 5% (w/v) dextrose. A volume of diluent equal to the calculated volume of MEDI4736 to be added to the IV bag must be removed from the bag prior to addition of MEDI4736. The calculated volume of

CONFIDENTIAL

MEDI4736 is then added to the IV bag, and the bag is mixed by gentle inversion to ensure homogeneity of the dose in the bag.

Example: For a 1500 mg dose (for subjects > 30 kg in weight), 30 mL of MEDI4736 is to be diluted in a 250 mL IV bag. First, 30 mL of diluent is removed from the IV bag, and then 30 mL of MEDI4736 is added to the bag. The bag is mixed by gentle inversion to ensure homogeneity of the dose in the bag.

MEDI4736 does not contain preservatives, and any unused portion must be discarded.

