Dose Level	PLD [mg/m ² IV]	MEDI4736 [IV]	Motolimod [mg/m ² SC]
-1	40	450 mg Q4W	2.0
0a (Starting Level)	40	3 mg/kg Q2W (equivalent to 450 mg Q4W)	2.5
0b	40	1500 mg Q4W	2.0
+1	40	1500 mg Q4W	2.5

3. A fixed dosing schedule for MEDI4736 was added for all subjects except for those in the cohort that was already started prior to Amendment 1 (i.e., dose level 0a).

Rationale for fixed dosing of MEDI4736:

Currently, the recommended dosing schedule for MEDI4736 is 20 mg/kg every 4 weeks (Q4W). The fixed dosing in this protocol for MEDI4736 (1500 mg Q4W for the +1 and 0b dose levels) is based on data from PK models. Using population PK models, simulations indicated that both body weight-based and fixed dosing regimens of MEDI4736 yield similar median steady state PK concentrations with slightly less between-subject variability with fixed dosing regimens. A fixed dosing approach is preferred by the prescribing community due to ease of use and reduced dosing errors. Given expectation of similar PK exposure and variability, it is considered feasible to switch to fixed dosing regimens. Based on an average body weight of 75 kg, a fixed dose of 1500 mg Q4W MEDI4736 is equivalent to 20 mg/kg Q4W or 10 mg/kg Q2W.

The 1500 mg dosing of MEDI4736 is recommended only for subjects with > 30 kg body weight due to endotoxin exposure. Subjects with a body weight ≤ 30 kg are not eligible for enrollment in the current study. If a subject's body weight drops to ≤ 30 kg while on the study, the MEDI4736 dose will be weight based as long as the body weight remains ≤ 30 kg (see Section 6.3.3.2).

Rationale for addition of dose level 0b:

If the starting dose level 0a does not clear and dosing de-escalates to -1, dose level 0b will continue to accrue subjects according to the 3 + 3 design (in addition to the cohort at the dose level -1) because it represents a de-escalation of motolimod from 2.5 to 2.0 mg/m². The 1500 mg of MEDI4736 is supported by the fact that there is no dose response for toxicity for anti-PD-1 and anti-PD-L1 antibodies, and even half the clinical dose of MEDI4736 would be above

saturation of the receptor. Therefore, it would be safe to reduce the motolimod dose (from 2.5 to 2.0) but maintain the currently recommended 1500 mg dose for MEDI4736.

If dose level 0a does clear and dosing escalates to +1, dose level 0b will also continue to accrue subjects according to the 3 + 3 design (in addition to the cohort at the dose level +1).

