3.1.7 Treatment Arms and Treatment Schema

All subjects will be treated with pegylated liposomal doxorubicin (PLD) intravenously, MEDI4736 intravenously and motolimod (pre Amendment 2 only) subcutaneously during each 28-day cycle according to the treatment schedule below. On days with concurrent motolimod and MEDI4736 dosing, motolimod administration will occur 30-60 minutes after the end of the MEDI4736 infusion (pre Amendment 2 only).

PER Amendment 2, motolimod dosing will be discontinued for all subjects. At the time of Amendment 2, Phase 1 is completed, and Phase 2 will be initiated at the +1 dose level (PLD 40 mg/m², MEDI4736 1500 mg Q4W). Subjects who initiated treatment during Phase 1 will continue the trial at their respective doses levels for PLD and MEDI4736; however, motolimod will be discontinued.

PER Amendment 2 Treatment Schedule for Cohort at Dose Level 0a only	
DAY	CYCLES 1 – 12
1	Pegylated liposomal doxorubicin (IV)
3	MEDI4736 (IV)
17	MEDI4736 (IV)

PER Amendment 2 Treatment Schedule for all Subjects Except Cohort at Dose Level 0a	
DAY	CYCLES 1 – 12
1	Pegylated liposomal doxorubicin (IV)
3	MEDI4736 (IV)

Pre Amendment 2 Treatment Schedule for Cohort at Dose Level 0a only (see note below)		
DAY	CYCLES 1 – 3	CYCLES 4 – 12
1	Pegylated liposomal doxorubicin (IV)	Pegylated liposomal doxorubicin (IV)
3	MEDI4736 (IV) + Motolimod (SC)	MEDI4736 (IV) + Motolimod (SC)
10	Motolimod (SC)	n/a
17	MEDI4736 (IV) + Motolimod (SC)	MEDI4736 (IV) + Motolimod (SC)

[figure not shown]
Pre Amendment 2 Treatment Schedule for all Subjects Except Cohort at Dose Level 0a		
DAY	CYCLES 1 – 3	CYCLES 4 – 12
1	Pegylated liposomal doxorubicin (IV)	Pegylated liposomal doxorubicin (IV)
3	MEDI4736 (IV) + Motolimod (SC)	MEDI4736 (IV) + Motolimod (SC)
10	Motolimod (SC)	n/a
17	Motolimod (SC)	n/a

Phase 1 Dose escalations and de-escalations for the determination of the MTD (or highest tolerable dose tested) will be performed based on the available dose levels and the respective rules for a standard 3 + 3 study design, as per Dose Level Table and Schema below:

Dose Level Table			
Dose Level	Pegylated liposomal doxorubicin [mg/m² IV]	MEDI4736 [IV]	Motolimod [mg/m² SC] Pre Amendment 2 only*
-1	40	450 mg Q4W	2.0
0a (Starting Level)	40	3 mg/kg Q2W (equivalent to 450 mg Q4W)	2.5
0b	40	1500 mg Q4W**	2.0
+1	40	1500 mg Q4W**	2.5

Q2W = every 2 weeks; Q4W = every 4 weeks

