 **Note for fixed dose of 1500 mg MEDI4736: If a subject's body weight drops to ≤ 30 kg while on the study, the MEDI4736 dose will be weight based as long as the subject's body weight remains ≤ 30 kg. See Section 6.3.3.2.
 *PER Amendment 2, motolimod dosing will be discontinued for all subjects

Note: Per Amendment 1, dose level 0 was renamed as 0a, and dose level 0b was added to Phase 1. Depending on the timing of Amendment 1, dose level 0b cohort could be running concurrently with the cohort at dose level 0a, -1, or +1. The dosing for the cohort in dose level 0a will continue per the protocol prior to Amendment 1 (i.e., MEDI4736 at 3 mg/kg Q2W); however, escalation or de-escalation dosing will be conducted according to Amendment 1.

For detailed definitions of DLT and MTD see Section 3.1.9.

Phase 2 subjects will be treated at the MTD level determined in Phase 1. See Sections 3.1.5 and 3.1.6 for the number of subjects to be enrolled.

Subjects will be followed on study for 90 days after the last drug administration and off-study every 3 months thereafter for 3 years from initiation of treatment (see Section 3.1.16).

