6.4 Estimated Study Drug Requirements for Motolimod and MEDI4736

Drug	Calculation	Required Quantity
Motolimod	53 subjects X 12 cycles 53 subjects Cycles 1 - 3: 3 vials per cycle = 477 vials 6 subjects (Dose Level 0a): 2 vials per Cycles 4-12: 108 vials 47 subjects (all others): 1 vial per Cycles 4-12: 423 vials Total = 1,008 vials Total + 20% overage: 1,210 vials PER Amendment 2, motolimod dosing will be discontinued for all subjects.	1,210 Vials
MEDI4736	53 subjects X 12 cycles: 6 subjects (Dose Level 0a): 4 vials per cycle: 288 vials 6 subjects (Dose Level -1): 1 vial per cycle: 72 vials 41 subjects (all others): 3 vials per cycle: 1476 vials Total = 1836 vials Total + 20% overage: 2,203	2,203 Vials
MEDI4736	Additional MEDI4736 for optional study treatment extension per Section 3.1.12 Assumptions: 15% of subjects will continue for 12 cycles beyond Core Study	343 vials

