6.5 Drug Overdose Management

Any overdose with PLD should be managed according to the package insert/ prescribing information.

Any overdoses with motolimod and MEDI4736 should be managed symptomatically. There are no known antidotes available for these drugs. An overdose is defined as a subject receiving any dose in excess of that specified in this protocol by >10%. All such overdoses must be reported, with or without associated AEs/SAEs, according to Section 7.1.2.2.

CONFIDENTIAL

7 Administrative, Legal & Ethical Requirements

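### The MEDI4736 preparation instruction for everyone outside level 0a is 1500 mg, with no exception for level -1, which the dose-level table sets at 450 mg; the passages need reconciling

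*Protocol*

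**What the plan says.** The dose-level table appears in the protocol synopsis, in Sections 2.1 and 3.1.7, and in SAP Section 2.2. In each place the MEDI4736 dose is 450 mg Q4W at level -1, 3 mg/kg Q2W at level 0a, and 1500 mg Q4W at levels 0b and +1. The level 0a entry reads "3 mg/kg Q2W (equivalent to 450 mg Q4W"), and the note below the table in Section 3.1.7 repeats it: "The dosing for the cohort in dose level 0a will continue per the protocol prior to Amendment 1 (i.e., MEDI4736 at 3 mg/kg Q2W"). Section 2.1 (Rationale for Amendment 1) describes the fixed dose as "1500 mg Q4W for the +1 and 0b dose levels".

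Preparation is split in two. Section 6.3.3.1 is for level 0a only. It gives a formula that takes the assigned mg/kg dose, followed by one example: "For a subject weighing 80 kg and dosed at 10 mg/kg, 16 mL". Section 6.3.3.2 is for all other subjects and for the optional extension. It states: "Subjects will receive a fixed dose of MEDI4736: 1500 mg Q4W for subjects > 30 kg". Its only worked example is 30 mL for 1500 mg. It does not mention 450 mg.

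The supply estimate in Section 6.4 allots "6 subjects (Dose Level -1): 1 vial per cycle: 72 vials" and "6 subjects (Dose Level 0a): 4 vials per cycle: 288 vials".

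**The concern.** The preparation section is what a site pharmacist works from. Level -1 is outside level 0a, so Section 6.3.3.2 governs it by its own scope, and the protocol has no other preparation text for a 450 mg bag. A pharmacist who reads Section 3.1.7 and one who reads Section 6.3.3.2 would prepare different amounts for the same subject.

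A level -1 subject prepared under Section 6.3.3.2 would also receive what the table calls level 0b. Both levels have PLD 40 mg/m² and motolimod 2.0 mg/m², so MEDI4736 is the only thing that separates them.

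The level 0a text raises a weaker version of the same worry. Its single illustration is at a dose that no row of the table assigns, and the supply count for that level does not fit the table either.

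**Working it through.** **Inputs.** The concentration is 50 mg/mL and a vial holds 500 mg (Section 6.3.1). Doses are from the Section 3.1.7 table. The average weight of 75 kg is from Section 2.1. Level 0a has two infusions per 28-day cycle, on Days 3 and 17. Vial counts are from Section 6.4.

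**The plan's own figures reproduce.**
- Section 6.3.3.1 example: 10 × 80 / 50 = 16 mL.
- Section 6.3.3.2 example: 1500 / 50 = 30 mL.
- Level 0a equivalence in the table: 3 × 75 × 2 = 450 mg per four weeks.
- Supply: 288 + 72 + 1476 = 1836 vials; × 1.2 = 2203.

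The sums are therefore right. The issue is which dose goes into them.

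**Level -1.**

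| Source | Dose per cycle | Volume | 500 mg vials |
|---|---|---|---|
| Dose-level table, 3.1.7 | 450 mg | 450 / 50 = 9 mL | 1 |
| Preparation, 6.3.3.2 | 1500 mg | 1500 / 50 = 30 mL | 3 |
| Supply, 6.4 | not stated | not stated | 1 |

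The ratio is 1500 / 450 = 3.33. One vial per cycle fits 450 mg and cannot supply 1500 mg, so Section 6.4 follows the table here.

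**Level 0a, worked example.** At 80 kg the formula in Section 6.3.3.1 gives 3 × 80 / 50 = 4.8 mL at the table's dose. The example shows 16 mL, and 16 / 4.8 = 3.33.

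**Level 0a, supply.**
- Four vials per cycle over two infusions is two vials per infusion.
- At 75 kg, 3 mg/kg is 225 mg, so one vial per infusion and two per cycle.
- One vial is enough at 3 mg/kg up to 500 / 3, about 166 kg.
- Two vials per infusion does fit 10 mg/kg at 75 kg (750 mg).
- With two vials per cycle, level 0a needs 6 × 12 × 2 = 144 vials. The total is 144 + 72 + 1476 = 1692, or 2030 with 20% overage. The stated figure is 2203, so the difference is 173 vials, about 8%.

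Section 6.4 thus agrees with the table for level -1 but not for level 0a.

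**The case against.** Much of the case on the other side stands.

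- **The level 0a example is not an instruction.** It is labelled as an example and conditional on 10 mg/kg, its arithmetic is correct, and the formula above it returns 4.8 mL once 3 mg/kg is entered. The 3 mg/kg dose is stated repeatedly elsewhere. A reader might infer that the preparation section orders 3.3 times the table dose at two of the four levels. Only level -1 has two conflicting instructions.
- **Overdose is not established.** Section 6.5 says: "An overdose is defined as a subject receiving any dose in excess of that specified in this protocol by >10"%. A reader might conclude that 1500 mg at level -1 meets this definition. Against the table it is 233% above; against Section 6.3.3.2 it is exactly as specified. The definition also concerns a dose that was received, and the documents show no such case. The label would presume that the table governs.
- **Level -1 was probably never opened.** Section 2.1 makes level -1 the branch if level 0a does not clear, and +1 the branch if it does. Phase 2 started at +1. The documents do not state the enrolment by level, and the escalation schema is not shown, so this is an inference.
- **Level 0a core dosing had probably ended before Amendment 4.** SAP Section 2.2 implies that Phase 2 had begun by 18 August 2016. If every level 0a subject had started by then, the last scheduled infusion (Day 325) falls no later than 8 July 2017 without delays. Amendment 4 is dated 8 September 2017.
- **The escalation argument is largely moot.** A reader might infer that the conflict undermined the choice of dose level. Escalation was finished by Amendment 2, and nothing shows that any subject was prepared at the wrong amount.
- **The supply figure is an estimate with overage.** It errs towards surplus and has no inferential consequence.

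What the objection does not remove is the level -1 contradiction. The intended scope of 1500 mg can be inferred from Section 2.1 and from the table's footnote marks on the 0b and +1 rows, but Section 6.3.3.2 does not say it. The 1500 mg dose in the optional extension (Section 8.9) is meant for all subjects and is not part of the conflict.

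**Conclusion.** The contradiction is real and limited. For level -1, Sections 3.1.7 and 6.3.3.2 give operative instructions that differ 3.33-fold (9 mL against 30 mL), and Sections 2.1 and 6.4 are consistent with the first. For level 0a, the sole worked example and the vial count do not match the table's 3 mg/kg. These are secondary: the formula is sound, and the supply effect is 173 vials on 2203.

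The ratio needs no assumption beyond the stated doses; the volumes also use the nominal 50 mg/mL. The 0a vial count assumes one 500 mg vial per infusion, which holds at the protocol's 75 kg average and up to about 166 kg. That current exposure is probably small rests on Phase 1 having been complete at Amendment 2 and on the Section 2.1 branching; the documents do not confirm that level -1 was empty. They support neither a finding that anyone was misdosed nor a decision on which dose is the right one.

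**What to change.** The sponsor should:

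- reconcile Sections 3.1.7, 6.3.3.1, 6.3.3.2 and 6.4, and state which preparation text applies to level -1;
- align the level 0a worked example, vial count and supply total with the reconciled dose;
- check dispensing records for level 0a, and for level -1 if anyone was enrolled there, against the reconciled dose, and record the result, including a plain statement if level -1 was never opened.

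The cost is some wording, a few supply figures in one amendment, and a review of existing dispensing logs. No change to the design or the analysis is needed, and no dose is proposed here.
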